10.3.5 Procedures for Early Termination

If a patient withdraws or is removed from the study for any reason, all early termination procedures should be completed per the Schedules of Study Assessments ([Table 1](#) and [Table 2](#)). Reason for withdrawal, date of the discontinuation, and date of the last dose of IP should be recorded in source documents and in the appropriate section of the eCRF. IP assigned to the withdrawn patient may not be assigned to another patient.

The medical monitor and study chair should be consulted prior to the withdrawal of the study patient, except in the case of a medical emergency. Written notice (regardless of cause) is to be provided to the medical monitor within 48 hours of the withdrawal. At the time of discontinuation, every effort should be made to ensure all relevant procedures and evaluations scheduled for the final study visit are performed. At the time of discontinuation, a self-addressed stamped shipper will be sent to the patient for returning of the ActiGraph GT9x and all accessories.

10.4 Patient Replacement

Patients will not be replaced.

10.5 Suspension or Termination of Study

If, in the opinion of the study chair and the medical monitor, clinical observations in the study suggest that it may be unwise to continue, the study may be suspended. The study chair will request a DSMB meeting and consult with the sponsor. If the study chair, medical monitor, DSMB, and sponsor agree that safety concerns warrant termination of the study, the sponsor will terminate the study. A written statement fully documenting the reasons for such a termination will be provided to investigators, IRBs/IECs, and regulatory authorities, if required.

NS Pharma, Inc. has the right to terminate an investigator's participation in the study and remove all study materials from a clinical site. A written statement will be provided to the investigator, the IRB/IEC, and regulatory authorities, if required.

Possible reasons for termination of the study at a clinical site include, but are not limited to:

- Unsatisfactory enrollment with respect to quantity or quality
- Inaccurate or incomplete data collection on an ongoing basis
- Falsification of records
- Failure to adhere to the protocol

If any SAEs or non-SAEs have occurred at such a clinical site, all documentation relating to the event(s) must be obtained.

11 SAFETY PROCEDURES AND PROCESSES

11.1 Definition of Adverse Events and Adverse Drug Reactions

An AE is any untoward medical occurrence in a patient or clinical investigation patient administered a pharmaceutical product, including control, and which does not necessarily have a causal relationship with treatment. This includes any untoward signs or symptoms experienced by the patient from the time of consent until completion of the study.

AEs may include, but are not limited to:

- Any unfavorable and unintended sign (including an abnormal laboratory finding), symptom, or disease temporally associated with the use of a medicinal product, whether or not considered related to the medicinal product
- Any new disease or exacerbation of an existing disease
- Any deterioration in non-protocol-required measurements of laboratory value or other clinical test (e.g., ECG) that results in symptoms, a change in treatment, or discontinuation from IP

Disease signs, symptoms, and/or laboratory abnormalities already existing prior to the use of the product are not considered AEs after treatment, unless they reoccur after the patient has recovered from the preexisting condition or in the opinion of the investigator, they represent a CS exacerbation in intensity or frequency. If CS worsening from baseline is noted, the changes will be documented in the AE source document and the eCRF.

TEAEs are defined as any AE or worsening of an existing condition after initiation of the IP and through 30 days after completion of study participation.

A suspected adverse reaction is any noxious and unintended response for which there is a reasonable possibility that the drug caused the AE. For the purposes of Investigational New Drug safety reporting, “reasonable possibility” means there is evidence to suggest a causal relationship between the drug and the AE. A suspected adverse reaction implies a lesser degree of certainty about causality than adverse reaction, which means any AE caused by a drug.

An AE and/or a suspected adverse reaction is considered “unexpected” if it is not listed in the IB or is not listed at the specificity or severity that has been previously observed. As viltolarsen is approved in the US, the US package insert will be referenced for the purposes of expedited

reporting to the FDA and US sites. During the course of the study, the IB will be updated on an ongoing basis with new important safety information.

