5.3 Study Duration and Dates

The expected study duration for each patient is approximately 56 weeks. The Pretreatment Phase will last approximately 28 days (inclusive of Screening Visit and Pretreatment Visit). The Treatment Phase will last approximately 48 weeks. The follow-up phase is 30 days.

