9 STUDY PROCEDURES

9.1 Time and Events Schedule

The Schedules of Study Assessments are described in [Table 1](#) and [Table 2](#); however, a patient can be seen at any time for reasons of safety. Study events are divided into the following phases:

- Pretreatment Phase:
 - From execution of informed consent/HIPAA authorization/assent until Day -1
- Treatment Phase:
 - From Day 1 (first infusion) until Week 48 (last infusion)
- End-of-Treatment Phase:
 - The 30-day interval (including Week 49) beginning after completion of the 48-week Treatment Phase and ending after a final phone call for collection of any information about AEs, concomitant medications, and actigraphy for all patients

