10.3.2 Follow-up Phone Call

Patients will have a phone call conducted by a member of the site study staff, 30 days (± 3 days) following the last IP infusion, to assess AEs; actigraphy; and medical, surgical, medication, and treatment review. Any AE(s) that is unresolved will be followed up by the site (investigator or designee) for as long as medically indicated. The clinical research organization (CRO) retains the right to request additional information for any patient with ongoing AEs at the end of the study, if judged necessary.

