10.3.4 Early Termination or Withdrawal from the Study

A patient (or the legal guardian acting on behalf of the patient) is free to withdraw consent and discontinue participation in the study at any time, without prejudice to further treatment, according to standard clinical practice. Study participation may be discontinued at any time at the discretion of the investigator or sponsor. The following may be justifiable reasons for removing a patient:

- Withdrawal of consent by the patient/legal guardian
- Failure to comply with the protocol
- Lost-to-follow-up
- Illness, condition, or procedural complication (including AEs) affecting the patient's ability to participate or requiring prohibited medication
- In the investigator's judgment, it is deemed in the best interest of the patient to discontinue his/her participation in the study
- The investigator, sponsor, Data and Safety Monitoring Board (DSMB), and/or regulatory authority terminates the study
- Any other reason

A Patient Completion/Discontinuation eCRF, describing the reason for discontinuation, must be completed for any discontinued or withdrawn patient regardless of reason. If a patient withdraws from the study or if the study is prematurely terminated, the investigator or designee will contact the patient or the patient's legal guardian **within 30** days after withdrawal or termination to assess any AEs. The investigator will be asked to follow all SAEs until the event returns to baseline or until the investigator determines that follow-up is no longer medically necessary.

Patients who are withdrawn from the study may not re-enter.

The following assessments should be performed at the time of early termination:

- Medical history (any updates will be recorded)

- Height and weight
- Vital signs
- Physical and neurological examination
- 12-lead ECG
- Renal ultrasound
- Echocardiogram
- Hematology
- Chemistry
- First morning void urinalysis

Note: Analysis of the first morning void urine sample will include urine dipstick protein to be performed at the site.

- Urine cytology (utilizing a urine sample collected on-site)
- Respiratory assessments
 - FVC
 - FEV1
 - PEF
 - PCF
- Function and strength
 - NSAA
 - Vignos scale
 - Hand-held dynamometer
 - Brooke scale
 - PUL
- Patient reported outcomes
 - PODCI
 - PARS III Questionnaire
- AE review
- Data upload from ActiGraph GT9x

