11.7 Reporting

11.7.1 Adverse Event Reporting

All AEs occurring during the course of the study (starting from signing informed consent to study completion) will be collected on the AE eCRF. Each AE is to be evaluated for duration,

severity, seriousness, and causal relationship to the IP. For each AE, the following information will be recorded:

- Description of the event (e.g., headache)
- Date of onset
- Date of resolution (or that the event is continuing)
- Action taken as a result of the event
- Seriousness of the event
- Severity of the event
- Outcome of the event
- Investigator's assessment of relationship to IP

A cluster of signs and symptoms that results from a single cause should be reported as a single AE (e.g., fever, elevated WBC, cough, abnormal chest X-ray, etc., can all be reported as "pneumonia").

The investigator will carefully evaluate the comments of the patient and the response to treatment in order that he/she may judge the true nature and severity of the AE. The question of the relationship of AE to IP administration should be determined by the investigator or study physician after thorough consideration of all facts that are available.

CS changes from time of ICF will be documented as AEs on the AE eCRF. CS changes are physical findings that have medical relevance and may result in an alteration in medical care.

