11.7.3 Serious Adverse Event Reporting

All SAEs occurring from the time of informed consent until the follow-up telephone call, 30 days following the last administration of IP, must be reported to the designated CRO within 24 hours of the knowledge of the occurrence. This includes death due to any cause and whether or not the SAE is deemed drug-related or expected. After the 30-day reporting window, any SAE that the investigator considers related to IP must also be reported.

To report the SAE, the investigator is to complete the SAE form electronically in the electronic data capture (EDC) system for the study. If the event meets serious criteria and it is not possible to access the EDC system, the investigator is to send an email, phone, or fax the event to the designated CRO within 24 hours of awareness. When the EDC system becomes available, the SAE information must then be entered within 24 hours of the system becoming available.

The investigator is required to submit SAE reports to the IRB or IEC in accordance with local requirements.

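### The TEAE window does not match the period over which AEs are collected, and the AE contact after withdrawal has no earliest date

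*Combined protocol and SAP*

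**What the plan says.** Section 11.1 defines a TEAE as an AE, or the worsening of an existing condition, arising "after initiation of the IP and through 30 days after completion of study participation". The same section describes AEs as running "from the time of consent until completion of the study", and Section 11.7.1 collects them on the eCRF "starting from signing informed consent to study completion".

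For a patient who finishes treatment, the last scheduled AE contact is the Section 10.3.2 telephone call, 30 days (±3) "following the last IP infusion, to assess AEs". Section 9.1 describes the last phase as "ending after a final phone call for collection of any information about AEs". Section 5.3 counts follow-up within each patient's study duration: "The follow-up phase is 30 days". Section 11.10 stops eCRF recording of unresolved AEs after the last AE assessment.

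Section 11.7.3 requires all SAEs, whatever their cause, up to the call 30 days after the last dose. Beyond that: "After the 30-day reporting window, any SAE that the investigator considers related to IP must also be reported".

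For a patient who withdraws, Section 10.3.4 requires the site to make contact within 30 "days after withdrawal or termination to assess any AEs". It also lists assessments for early termination, including AE review and laboratory tests.

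Sections 12.5.1 and 12.5.3 summarise TEAEs by relationship to IP, among other breakdowns.

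**The concern.** The window that defines a primary endpoint should be one over which events are actually sought. Here the definition can run beyond the last AE contact. In that stretch, the only events that must be reported are those both serious and judged related, and relationship is itself a variable in the TEAE tables.

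The second problem is the contact after withdrawal. It is tied to withdrawal, not to the last dose, and only its latest date is set, so a call the next day complies. Patients who finish are asked about roughly the first 30 days after the last dose, while patients who leave may be asked about very little of it. Under Section 10.4 patients are not replaced, so one withdrawal is 1/20 = 5% of the safety denominator.

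**Working it through.** **Planning figure.** Section 12.2 gives at least 95% probability of seeing an adverse drug reaction of 15% incidence with 20 patients. 1 − 0.85^20 = 0.961, so the statement is correct.

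**Day count for completers (nominal schedule).**
- Last infusion (Week 48): 1 + 47 × 7 = Day 330.
- Week 49 visit: Day 337.
- Follow-up call: 330 + 30 = Day 360, range 357 to 363. AE collection ends here.

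The end of the TEAE window depends on what completion of participation means:

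| Completion means | TEAE window ends | Days beyond the call |
|---|---|---|
| Final call | Day 390 (387 to 393) | 30 |
| Week 49 visit | 337 + 30 = Day 367 | 367 − 363 = 4 to 367 − 357 = 10 |
| Last dose | 330 + 30 = Day 360 | at most 360 − 357 = 3 |

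On the first reading the window closes 57 to 63 days after the last dose, and the part without routine collection is 30/390 = 7.7% of it.

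**Withdrawn patients.** One compliant contact on day d after withdrawal covers d/30 of the following 30 days: day 1 gives 3%, day 7 gives 23%, day 15 gives 50%. The completers' call covers 27 to 33 days after the last dose. The contrast is greatest when withdrawal closely follows the last infusion.

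**Illustrative event counts.** Section 2.3.3 reports 59 TEAEs in 16 patients over 24 weeks in Study NS-065/NCNP-01-201.
- Rate: 59/(16 × 24) = 0.154 per patient-week.
- Over 30 days: 0.154 × 30/7 = 0.66 per patient, or about 13 in 20 patients.
- Over 4 to 10 days: 0.154 × 20 × 4/7 = 1.8 to 0.154 × 20 × 10/7 = 4.4.
- Over 0 to 3 days: 0 to 0.154 × 20 × 3/7 = 1.3.
- High-dose cohort alone (36 TEAEs; 8 patients per Section 2.1.1): 36/(8 × 24) × 30/7 = 0.80 per patient, or about 16 in 20 over 30 days.

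These figures assume that the rate seen during the study's 24 weeks continues after dosing stops. The documents do not establish that.

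**Effect on the planning figure.** Assume a constant hazard, with 15% incidence over 390 days and observation for 360. Observable incidence is 1 − 0.85^(360/390) = 13.9%. The probability of at least one event in 20 patients is then 1 − 0.85^(20 × 360/390) = 0.950, against 0.961.

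**The case against.** The best defence is that Section 11.1 simply names the wrong anchor. Sections 10.3.2 and 11.7.3 both work to about 30 days after the last dose. If that was the intended TEAE window, little or nothing within it is lost for completers. Section 11.1 also ends AEs at study completion, so it can be argued that a new event after completion is not an AE and cannot be a TEAE. Both arguments have force, but they show that the section disagrees with itself; they do not settle which window applies. Section 5.3.1 defines the end of the study, not the completion of one patient's participation.

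Withdrawn patients are also better covered than Section 10.3.4's contact rule alone suggests. The early-termination visit includes AE review, all-cause SAE reporting still runs to 30 days after the last dose, and Section 10.3.2 does not expressly restrict its call to completers. This stands. It narrows the concern to active ascertainment, mainly of non-serious AEs. Nothing says that a withdrawn patient must receive the day-30 call as well as the Section 10.3.4 contact.

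Section 12.1 announces a separate SAP that would supersede the protocol on analysis. It is not in the material reviewed and may restate the TEAE window. It could not recover events missed because a contact was made too early.

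Three stronger inferences are tempting and not supported:
- That about 13 TEAEs will be lost. This needs the widest reading of completion and a rate carried past the end of dosing, from a study of boys aged 4 to under 10.
- That the table by relationship will be distorted. Section 11.7.3 is a reporting duty, and the plan does not say that late related SAEs enter the TEAE tables. Study 201 and its extension reported no apparent drug-related SAEs, so distortion is possible but not shown.
- That patients usually leave because of an event. Section 10.3.4 lists AEs among possible reasons, but Section 2.3.3 reports no AE leading to drug discontinuation in the Phase 1/2 study, Study 201 or its extension.

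**Conclusion.** The inconsistency is real and should be corrected. The TEAE window and the AE collection period differ by about 30 days if completion means the final call, by 4 to 10 days if it means Week 49, and by at most 3 days if it means the last dose. Sections 5.3 and 9.1 favour the first reading without defining it for the individual patient. At the pooled Study 201 rate this is 0 to about 13 events in 20 patients, which is an illustration and not an estimate.

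The contact after withdrawal is a separate defect that holds on any reading: a compliant contact can leave almost all of the period after the last dose without active ascertainment of non-serious AEs.

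A reader might infer a biased comparison or an invalid sample size. Neither follows. The trial has one arm, the plan does not compare AEs with the natural history controls, and the planning probability moves only from 0.961 to 0.950 under the assumptions shown. The consequence is a TEAE incidence whose observation window is unclear and can differ from patient to patient.

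**What to change.** 1. In Section 11.1, define a TEAE as onset or worsening from the first IP dose through 30 days after the last IP dose.
2. In Section 10.3.4, time the AE contact for withdrawn patients no earlier than 30 days after the last IP dose, or at withdrawal if that is later. Section 10.3.5 already records the date of the last dose.
3. Have this contact and the completers' call in Section 10.3.2 ask about the whole 30-day window, for example with a tolerance of 0 to +3 days. With ±3 days, a call on day 27 leaves up to 3 days uncollected.
4. List IP-related SAEs with onset after the window separately from the TEAE counts.

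The cost is wording in Sections 11.1, 10.3.2 and 10.3.4, a matching edit to the call window in Table 2, and the timing of one call. No visit is added.

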11.2 Definition of a Serious Adverse Event

An AE is serious when the patient outcome is:

- Death
- Life-threatening (see below for expanded definition)
- Hospitalization (initial or prolonged)
- Disability or permanent damage (see below for expanded definition)
- Congenital anomaly/birth defect
- Important medical events that, based upon appropriate medical judgment, may jeopardize the patient and may require medical or surgical intervention to prevent one of the outcomes listed above

Life-threatening experience: Any AE that places the patient, in the view of the site investigator, at immediate risk of death from the AE as it occurred, i.e., does not include an AE that, had it occurred in a more severe form, might have caused death.

Any hospital admission with at least 1 overnight stay will be considered an inpatient hospitalization. However, emergency room visits that do not result in admission to the hospital should be evaluated for one of the other serious outcomes (e.g., life-threatening; required intervention to prevent permanent impairment or damage; other serious medically important event).

Hospitalization for an elective or outpatient procedure will not be considered an SAE. However, unexpected complications and/or prolongation of hospitalization that occur during elective or outpatient surgery should be recorded as AEs and assessed for seriousness. Admission to the hospital for social or situational reasons (e.g., no place to stay, live too far away to come for hospital visits) will not be considered inpatient hospitalizations.

Disability or permanent damage: Any AE that results in a substantial disruption of a patient's ability to conduct normal life functions, i.e., the AE resulted in a significant, persistent or permanent change, impairment, damage, or disruption in the patient's body function/structure, physical activities, and/or quality of life.

Important medical events that may jeopardize the patient and may require medical or surgical intervention to prevent one of the outcomes listed above: an AE that may not result in death, be life-threatening, or require hospitalization may be considered an SAE when, based upon appropriate medical judgment, it may jeopardize the patient and may require medical or surgical intervention to prevent one of the outcomes listed above.

11.3 Severity

It is the investigator's responsibility to assess the intensity (severity) of an AE.

The severity of the AE will be characterized and recorded as "mild, moderate, severe, life-threatening, or death" according to the following definitions: The CTCAE version 4.03 guidelines for severity assessments will be used to grade AEs for this study (available at evs.nci.nih.gov/ftp1/CTCAE/About.html). The CTCAE version 4.03 listed guidelines for severity assessment are:

- Mild: Asymptomatic or mild symptoms; clinical or diagnostic observations only or intervention not indicated
- Moderate: Minimal, local, or noninvasive intervention indicated or limited age-appropriate instrumental activities of daily living (ADL)
- Severe: Severe or medically significant but not immediately life-threatening; or hospitalization or prolongation of hospitalization indicated; or disabling; or limiting self-care ADL
- Life-threatening: Life-threatening consequences or urgent intervention indicated
- Death: Death related to AE

Note: A severe AE need not be serious, and an SAE need not be severe.

11.4 Relationship

It is the investigator's responsibility to assess the relationship between the IP and the AE. The degree of "relatedness" of the AE to the IP may be described using the following scale:

- Not Related
 - **Not Related**: No temporal association and other etiologies are likely the cause.

- **Unlikely:** Event or laboratory test abnormality, with a time to drug that makes a relationship improbable (but not impossible). Diseases or other drugs provide plausible explanations.
- **Related**
 - **Possible:** Temporal association, but other etiologies are likely the cause. However, involvement of the IP cannot be excluded.
 - **Probable:** Temporal association, other etiologies are possible but unlikely. The event may respond if the IP is discontinued.
 - **Definite:** Established temporal association with administration of the IP with no other more probable cause. The event should resolve when the IP is discontinued and recur on re-challenge.

